10.6.2 Best Corrected Visual Acuity

BCVA in the study eye will be collected at baseline and at all data collection points defined for the study. Values will be recorded in the eCRF according to local practice (Snellen, LogMAR, EDTRS, etc.) along with scale name or method used to assess BCVA.

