4.3. Disease progression

Ocular medical history will be summarised descriptively in the Safety Population overall and not by the time windows specified. Needling procedures will be summarized in the Safety Population by the time windows indicated in Section 4.1. Anti-metabolite/anti-fibrotic use will be described during the stent implantation, during conjunctiva bleb revision (if applicable), during needling procedures (if applicable), and also when used alone. Anti-metabolite/anti-fibrotic use during needling procedures will be determined based on the date of each anti-metabolite/anti-fibrotic use and date of the needling procedure; the same date assumes that the anti-metabolite/anti-fibrotic was used in conjunction with the needling procedure. IOP lowering medications (oral) will be described at baseline and post-implantation in the Effectiveness Population by class of medication (carbonic anhydrase inhibitors or alpha-agonist hypotensive agent). Visual field exam will be summarised descriptively at baseline and for all time points of interest (as described in Section 4.1) in the Safety Population. All BCVA values will be converted to logarithm of the minimum angle of resolution (logMAR) units.³ To do this, Snellen values will be converted by taking the negative base 10 logarithm of the decimal. ETDRS letters will be converted to approximate Snellen scores by the following formula.

$$\text{Snellen} \cong \exp \left\{ \frac{1}{50} (\text{ETDRS} - 85) \right\}.$$

This will then be converted into logMAR units using the negative base 10 logarithm of the decimal as above. Any non-numerical BCVA values (i.e. including count fingers, hand movement, light perception and non-light perception) will also be converted to logMAR units as described below:⁴

Non-numerical BCVA value	LogMAR
Count fingers (CF)	1.8
Hand movement (HM)	2.3

Light perception (LP)	2.8
No light perception (NLP)	3.0

4.4. Change in IOP and number of topical IOP-lowering medications after XEN 45 gel stent implantation

Change in IOP from medicated baseline and change in the number of topical IOP-lowering medications will be summarised. Change in number of IOP-lowering medications will be made by examining the class of the medication as follows:

- Beta Blocking Agents
- Carbonic Anhydrase Inhibitors
- Parasympathomimetics
- Prostaglandin Analogues
- Sympathomimetics In Glaucoma Therapy

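### The ETDRS-to-Snellen formula uses the natural exponential where base 10 is needed, so ETDRS acuities come out at 43% of their logMAR value and are not comparable with Snellen or logMAR records

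*SAP*

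**What the plan says.** Protocol section 10.6.2 lets sites report acuity on whichever scale they use: "Values will be recorded in the eCRF according to local practice". Snellen, logMAR and ETDRS are named there as examples, and the scale or method is recorded with each value.

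SAP section 4.3 then requires a common scale: "All BCVA values will be converted to logarithm of the minimum angle of resolution (logMAR) units". It gives these rules:

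- For Snellen, "Snellen values will be converted by taking the negative base 10 logarithm of the decimal".
- For ETDRS, "ETDRS letters will be converted to approximate Snellen scores by the following formula". The formula is Snellen ≅ exp{(1/50)(ETDRS − 85)}. The next step is "This will then be converted into logMAR units using the negative base 10 logarithm of the decimal as above".
- Four non-numerical grades get fixed logMAR values: count fingers 1.8, hand movement 2.3, light perception 2.8 and no light perception 3.0.

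Protocol section 14.2.3 plans descriptive summaries of BCVA at baseline and at each time point of interest.

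**The concern.** The two ETDRS steps use different bases: a natural exponential first, then a base-10 logarithm. They do not cancel, and a stray factor of log10(e) stays in every converted value.

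The purpose of the conversion is to make records from different charts comparable. With this formula, an eye measured in ETDRS letters and an identical eye measured by Snellen get different logMAR values. Below 85 letters the ETDRS eye looks better than it is, and any loss over time shrinks by the same factor. If the recording method changes between visits, a change appears that did not happen. In a study of long-term performance and safety, understating visual loss favours the device.

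Routine checks may not catch this. SAP section 3.2 says the derivation code will be validated, but code checked against this SAP would pass with the wrong formula in it.

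**Working it through.** **Inputs.** From SAP section 4.3: decimal = exp{(L − 85)/50}, where L is the ETDRS letter score; logMAR = −log10(decimal); count fingers = 1.8. By assumption, not stated in either document: an ETDRS chart has 5 letters per line and 0.1 logMAR per line, so 0.02 logMAR per letter, with 85 letters at logMAR 0. The documents give no converted BCVA value, so there is no stated figure to reproduce.

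**As written.** logMAR = −log10(exp{(L − 85)/50}) = log10(e) × (85 − L)/50 = 0.4343 × (85 − L)/50 = 0.008686 × (85 − L).

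**With base 10.** logMAR = −log10(10^{(L − 85)/50}) = (85 − L)/50 = 0.02 × (85 − L).

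**Ratio.** 0.008686/0.02 = 0.4343 at every score except 85, where both give 0. The understatement is 1 − 0.4343 = 0.5657, or 57%.

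| Letters | Decimal, as written | logMAR, as written | Decimal, base 10 | logMAR, base 10 |
|---|---|---|---|---|
| 95 | 1.221 | −0.087 | 1.585 | −0.20 |
| 85 | 1.000 | 0.000 | 1.000 | 0.00 |
| 80 | 0.905 | 0.043 | 0.794 | 0.10 |
| 70 | 0.741 | 0.130 | 0.501 | 0.30 |
| 50 | 0.497 | 0.304 | 0.200 | 0.70 |
| 35 | 0.368 | 0.434 | 0.100 | 1.00 |
| 20 | 0.273 | 0.565 | 0.050 | 1.30 |
| 0 | 0.183 | 0.738 | 0.020 | 1.70 |

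**Change over time.** A 10-letter (2-line) loss gives 10 × 0.008686 = 0.087 as written and 10 × 0.02 = 0.20 with base 10.

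**Which base was meant.** Three things inside SAP section 4.3 point to base 10:

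1. The constants 85 and 50 give exactly 0.02 logMAR per letter with base 10. With exp they give 0.0087.
2. With base 10, 0 letters is 1.70, just short of the SAP's count-fingers value of 1.8. As written, 0 letters is 0.74, which is 1.06 logMAR units better than count fingers.
3. A Snellen decimal of 0.1 converts to −log10(0.1) = 1.00. As written, an eye that reads no ETDRS letters (0.74) scores better than that, and no ETDRS score can reach 1.00.

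**Change of method between visits.** Take 35 letters at baseline (0.43 as written) and a Snellen decimal of 0.1 later (1.00). These are the same acuity, yet the data show a loss of 1.00 − 0.43 = 0.57.

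**Effect on a pooled mean.** The documents do not give the share f of ETDRS records. Suppose the true mean is 0.30 for ETDRS and other eyes alike. The pooled mean is then 0.30 × (1 − 0.5657f):

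| Assumed ETDRS share | Pooled mean logMAR (true 0.30) |
|---|---|
| 10% | 0.283 |
| 25% | 0.258 |
| 50% | 0.215 |

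**The case against.** The algebra is not in dispute. The case on the other side is about reach, and most of it stands.

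- BCVA is not in the primary or secondary objectives, the success definitions or the listed outcome variables. It is summarised descriptively and no test on it is planned.
- The only 2-line criterion in the plan is clinical hypotony (Protocol section 10.9.2, SAP section 1.8). Nothing says it is derived from converted logMAR values, so the 0.087 figure does not show that hypotony or success is misclassified.
- Records already in Snellen or logMAR do not pass through the formula. The number of ETDRS records is unknown, and at a 10% share the illustrative mean moves only from 0.30 to 0.283.
- There is no error at 85 letters and little close to it. Above 85 the direction reverses: at 95 letters the eye looks worse than it is.
- The letter scale is not stated in the documents, and the SAP calls its conversion approximate. The count-fingers value does not formally contradict the formula, since 0.74 is still below 1.8.
- The distortion is a fixed factor and can be reversed from the recorded letters.

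These points limit the consequences but do not support the formula. Approximation does not explain a constant factor of 0.43. The Snellen comparison uses only the SAP's own conversions: as written, an eye that reads no letters scores better than a Snellen decimal of 0.1.

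**Conclusion.** The concern holds. The ETDRS conversion in SAP section 4.3 is wrong as written and nothing elsewhere in the documents corrects it. Apart from scores of exactly 85 letters, each ETDRS record is converted to 43% of its base-10 logMAR value, and within-eye changes on ETDRS are understated by 57%. ETDRS-derived values cannot be pooled with Snellen or logMAR records until the formula is changed.

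The factor of 0.4343 is pure algebra. Calling the base-10 value the correct one rests on the standard 0.02 logMAR per letter, which the SAP's own constants, its base-10 logarithm and its count-fingers value all support. The damage is confined to descriptive BCVA summaries, and its size there depends on an ETDRS share that the documents do not give.

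**What to change.** In SAP section 4.3, replace the formula with Snellen decimal = 10^{(ETDRS − 85)/50}. Simpler still, drop the intermediate step and set logMAR = (85 − ETDRS)/50. If any BCVA variable has already been derived with the printed formula, derive it again.

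Add three check values to the program validation: 85 letters gives 0.00, 35 letters gives 1.00 and 0 letters gives 1.70. It would also help to report how many BCVA records came from each scale.

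The formula change is one line of SAP text and one line of code. The acuity value and its scale are already captured for each record, so no new data are needed, and there is no reason to keep the present formula.

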14.2.4 Primary Objective

Change in IOP from medicated baseline and change in the number of topical IOP-lowering medications compared to baseline will be summarized descriptively at Year 3 after XEN 45 Gel Stent implantation in eyes from the Analysis Population with at least 3 years of follow-up data and were not treated with Diamox on the day when decision was taken to implant XEN 45 Gel Stent.

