1.3. Study Objectives

1.3.1. Primary objective

The primary objective of this study is to assess the performance of XEN 45 Gel Stent over the long term as assessed by the change in IOP compared to medicated IOP at baseline and the change in the number of topical IOP-lowering medications compared to baseline, 3 years after implantation.

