1.4. Key Variable Definitions

Qualified success of implantation of the XEN 45 Gel Stent will be defined as $\geq 20\%$ reduction from medicated baseline with no Secondary Surgical Intervention (SSI) for glaucoma and no clinical hypotony while staying on the same number or fewer topical IOP-lowering medications than at baseline.

Complete success of implantation of the XEN 45 Gel Stent will be defined as $\geq 20\%$ reduction from medicated baseline with no SSI for glaucoma and no clinical hypotony while taking no topical IOP-lowering medications.

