1.6. Study Design

This is a retrospective, non-interventional, observational, multi-centre, chart review study conducted in patients who underwent placement of the XEN 45 Gel Stent as a standalone procedure or in combination with phacoemulsification from 1 January 2014 to 1 October 2015.

For each eligible eye, all retrospective data available from baseline (i.e. day when decision was made to implant XEN 45 Gel Stent) until Last Visit (i.e. date of the last follow-up visit available prior to 1 October 2018 or date on which the patient had a SSI for glaucoma, whichever occurs first) are extracted from existing medical records into the electronic CRF (eCRF) in Dacima.

If both eyes from the same patient meet eligibility criteria, each eye is included in the study database with a unique identifier and eyes are paired in the electronic data capture system (EDC). See section 4 for how bilateral eyes included in the study are handled in the analyses.

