 - Persistent corneal decompensation / edema (>30 days)
 - Mild corneal decompensation / edema

[figure not shown]

-
- Moderate corneal decompensation / edema
 - Severe corneal decompensation / edema
 - Cyclodialysis
 - Endophthalmitis
 - Hyphema
 - ≥ 2 mm in height (layered) at any time; present or arising > 30 days postoperatively
 - Persistent hypotony: IOP < 6 mmHg, present at two consecutive visits postoperatively > 30 days apart
 - Clinical hypotony: vision reduction (2 lines or more) related to macular changes consistent with hypotony maculopathy (macular folds), optic disc edema, and/or serious choroidal detachments because of low IOP
 - Implant blockage in the anterior chamber
 - Implant exposure or extrusion
 - Implant fracture
 - Implant migration
 - Implant repositioning requiring surgical intervention
 - Implant touching iris
 - Implant touching cornea
 - Iridodialysis
 - Iritis (requiring treatment after the postoperative medication taper)
 - Macular edema
 - Ptosis
 - Retinal detachment
 - Suture abscess or other local infection
 - Vitreous hemorrhage
 - Any other adverse event that leads to permanent visual impairment or requires surgical or medical intervention to prevent permanent visual impairment

2. Sample Size

A sample size of 150 patient eyes was selected, as it is anticipated that this will allow for the inclusion of a minimum of 60 independent study eyes have at least 3 years of follow-up data without a SSI for glaucoma after the initial implant with XEN 45 Gel Stent. Based on the Allergan study MS-001, for month 36 the 95% confidence interval (CI) of the projected mean IOP reduction afforded by a sample of 60 study eyes is -7.2 to -4.0 mmHg. That is, the half-length of the interval is 1.6 mmHg, which provides a reasonable precision for the estimate of the projected mean reduction in IOP.

3. Data Handling

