These will be compared to baseline and will be summarised descriptively at months 12, 24, 36 and 48 after XEN 45 Gel Stent implantation in eyes from the Effectiveness Population. Analyses will only include those with available data at each of the time points of interest and those who were not treated with Diamox on the day when decision was taken to implant XEN 45 Gel Stent.

A paired t-test will be applied for statistical analysis in comparing the difference between post baseline to baseline values. The assumptions of the test are as follows:

- No significant outliers in the differences between time points (which can be tested by a scatter plot of the data)
- The distribution of the differences in the dependent variable between the two time points should approximately follow a normal distribution (which can be tested through the Shapiro-Wilk test)
- The dependent variable is measured on a continuous scale

If the assumptions of the t-test are heavily violated then the non-parametric analogue (Wilcoxon Signed-Rank test) should be used to test the difference between time points.

4.4.1. Success over the long term of following implantation of the XEN 45 Gel Stent

Number and proportion of eyes achieving a 20% reduction in IOP from medicated baseline, and number and proportion of eyes with an IOP between 6 and 18 mmHg, IOP between 6 and 17 mmHg, ..., down to IOP between 6 and 12 mmHg will be described by the time-windows described in Section 4.1 in eyes from the Effectiveness Population that did not undergo SSI for glaucoma, and were not treated with Diamox on the day when decision was taken to implant XEN 45 Gel Stent.

The number and proportion of eyes achieving qualified or complete success at each time point of interest (i.e. 12, 24, 36, 48 and >51 months) after XEN 45 Gel Stent implantation will be summarised descriptively. Analyses will be conducted in the Effectiveness Population.

The time from XEN 45 Gel Stent implantation to SSI for glaucoma will be described using Kaplan Meier curves.

4.5. Safety over the long term following implantation of the XEN 45 Gel Stent

Surgical complications and post-operative AESIs will be summarised descriptively using frequencies and percentages.

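### The Month 36 and Month 48 changes in IOP and medication count describe only eyes still free of secondary glaucoma surgery when measured; the SAP should label them so and add a sensitivity analysis that includes the operated eyes.

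*SAP*

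**What the plan says.** The primary objective (SAP 1.3.1; Protocol 6.1.1) is "to assess the performance of XEN 45 Gel Stent over the long term", measured by the change in IOP and in the number of topical medications 3 years after implantation. It does not mention SSI.

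Four rules decide which eyes contribute:

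- **End of data.** In SAP 1.6, Last Visit is the earlier of two dates: "date of the last follow-up visit available prior to 1 October 2018 or date on which the patient had a SSI for glaucoma". The Protocol synopsis (Sample Size) says that collection for an eye ends there.
- **Window.** SAP 4.1 takes the latest visit in Months 33 to 39 for Month 36, and in Months 45 to 51 for Month 48.
- **Analysis set, SAP 4.4.** "Analyses will only include those with available data at each of the time points of interest", and no Diamox at baseline.
- **Analysis set, Protocol 14.2.4.** The Year 3 summary is made "in eyes from the Analysis Population with at least 3 years of follow-up data", with the same Diamox exclusion.

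The sample-size text is more open about the restriction. SAP 2 counts towards its target of 60 the eyes that "have at least 3 years of follow-up data without a SSI for glaucoma after the initial implant with XEN 45 Gel Stent".

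SSI is handled as an outcome elsewhere. Both success definitions in SAP 1.4 require a 20% reduction "with no Secondary Surgical Intervention (SSI) for glaucoma and no clinical hypotony". SAP 4.4.1 and 4.6 plan Kaplan-Meier curves of time to SSI, and SAP 4.6 adds a summary of SSI by time window. The missing-data rules in SAP 3.4 say nothing about eyes with an SSI.

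**The concern.** The event that removes an eye from the primary changes is one that the plan itself counts as failure in its success definitions. The remaining eyes are selected partly on outcome. The mean therefore answers a narrower question than the objective: the change among eyes that reached the window without further glaucoma surgery. Protocol 14.3, on bias and limitations, does not list this selection.

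The boundary is also uneven. Under the SAP, an eye seen at Month 33 with an SSI at Month 35 contributes its pre-SSI value, while an eye with an SSI at Month 30 contributes nothing. The protocol's 3-year requirement would drop the first eye as well, so the two documents differ for an SSI between Months 33 and 36.

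SSI eyes are not ordinary missing data. The failure is known and dated, and Protocol 8.2.3 makes the SSI date, and IOP and medication count up to Last Visit, part of the minimum dataset. At stake is how a reader interprets the headline reduction: as the result for implanted eyes in general, or for eyes that did not need another operation.

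**Working it through.** **Step 1: the plan's own figure.** Inputs from Protocol 14.1: mean change -5.6 mmHg, SD 6.32 (the MS-001 Month 3 value, taken as the projection for Month 36), n = 60.

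Half-length = 1.96 × 6.32 / √60 = 1.60 mmHg, so the interval is -7.2 to -4.0. The stated figure reproduces.

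**Step 2: can an eye with an early SSI enter?** Take an SSI at Month 30. Last Visit is Month 30, so no IOP or medication value exists in Months 33 to 39. The eye fails the SAP's available-data rule and the protocol's 3-year rule. No other rule brings it back. The same holds at Month 48 for an SSI before Month 45.

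**Step 3: size.** Let p be the share of SSI eyes and d the mean change assigned to them. Then

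overall mean = (1 - p) × (-5.6) + p × d.

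Both p and d are assumptions. It is also assumed that -5.6 holds in SSI-free eyes; the documents do not say that the MS-001 value excludes SSI eyes.

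| p | d = 0: mean (shift) | d = -2: mean (shift) | d = +3: mean (shift) |
|---|---|---|---|
| 5% | -5.32 (0.28) | -5.42 (0.18) | -5.17 (0.43) |
| 10% | -5.04 (0.56) | -5.24 (0.36) | -4.74 (0.86) |
| 20% | -4.48 (1.12) | -4.88 (0.72) | -3.88 (1.72) |

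For d = 0 the shift is 5.6 × p. It would carry the mean to the planned upper limit of -4.0 at p = 1 - 4.0/5.6 = 28.6%.

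**Step 4: a summary that needs no assigned IOP.** If SSI eyes are ranked worst and the others are normal, the overall median is -5.6 + 6.32 × z(0.5/(1 - p)):

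- p = 5%: -5.6 + 6.32 × 0.066 = -5.18
- p = 10%: -5.6 + 6.32 × 0.140 = -4.72
- p = 20%: -5.6 + 6.32 × 0.319 = -3.59

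**Step 5: the paired test.** With 60 SSI-free eyes, t = 5.6 / (6.32/√60) = 6.9. In an extreme case of p = 30% at d = 0, about 26 zeros are added (60/0.7 = 85.7 eyes). The mean is 0.7 × (-5.6) = -3.92 and the SD is √(0.7 × 6.32² + 0.7 × 0.3 × 5.6²) = 5.88. Then t = 3.92 / (5.88/√85.7) = 6.2. The conclusion does not change.

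**Step 6: why raw counts are the wrong weights.** The plan accepts 60 analysable eyes out of 150 selected. Suppose, for illustration, that the other 90 are 15 SSI eyes and 75 lost without SSI. Adding the SSI eyes to the analysable eyes gives p = 15/(15 + 60) = 20%, against 15/150 = 10% of selected eyes observed to have an SSI. The true risk lies above 10%, since some lost eyes would have had an SSI later. The Kaplan-Meier estimate allows for that censoring; the raw proportion does not.

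**The case against.** The strongest reply is that the restriction is declared. Protocol 14.1 ties its target of 60 SSI-free eyes to the primary objective, and the Protocol synopsis and SAP 2 repeat the target. This stands in part: nobody who reads the sample-size text is misled. But that text sets an accrual target. Neither the objective nor SAP 4.4 states that the reported change applies only to eyes without SSI.

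A second reply is that SSI is already covered by the success proportions, the Kaplan-Meier curves and the window summary. This stands as far as it goes. A reader might infer that the plan conceals device failures, or that two series with different failure rates would look alike in the report. The documents do not support either inference, because those three outputs would differ visibly. They do not, however, alter the mean change or tell the reader of that table whom it describes.

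A third reply is that the size has no anchor. This stands. A reader might take the protocol's 30% of eyes with under 3 years of follow-up as a pool of SSIs and derive a large bias. That 30% extrapolates study discontinuation in MS-001, and nothing says how much of it, if any, is SSI.

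Finally, a reader might infer that the paired test is compromised. Step 5 shows no scenario in which its conclusion changes, and the protocol's primary summary is descriptive.

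**Conclusion.** The point holds as a mismatch between the objective and the eyes analysed. The Month 36 and 48 changes in IOP and medication count describe eyes still without SSI when measured; eyes operated on before the window are left out.

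The direction is conditional. The reported reduction is more favourable than the reduction over all implanted eyes if SSI eyes had done worse than retained eyes. That is expected, since the interventions listed in Protocol 10.8 are further glaucoma operations, but the documents give no IOP at SSI to confirm it. A flat statement that the primary result overstates performance therefore goes further than the documents allow.

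The size is unknown. With SSI eyes set to no change and -5.6 mmHg in the others, SSI shares of 5% to 20% shift the mean by 0.28 to 1.12 mmHg, against a planned half-length of 1.6 mmHg. No size can be given for medication count, because the documents hold no planning values for it.

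**What to change.** In SAP 4.4:

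1. **One cut-off and a true label.** Keep the planned analysis, but class any eye with an SSI before Month 36 (or 48) as an SSI eye, even if it has an earlier visit in the window. Label the estimate *eyes without SSI to Month 36 (48) and with data in the window*. Without the cut-off the label would be false for an eye seen at Month 33 with an SSI at Month 35.
2. **Counts beside the estimate.** Report the number of SSI eyes, the number without SSI but with no window data, and the Kaplan-Meier SSI risk at that month. Compute that risk in the same eyes (primary eye, no baseline Diamox), because SAP 4.6 places its curve in the Safety Population.
3. **A pre-specified sensitivity analysis including SSI eyes**, for both IOP and medication count. Give the median and quartiles with SSI eyes at the worst rank, and the mean with SSI eyes set to no change and to their last recorded pre-SSI value. Weight the SSI and SSI-free groups by the Kaplan-Meier risk, not by raw counts. State the assumptions: loss is unrelated to SSI risk, and SSI-free eyes with window data represent those without.

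The cost is SAP wording and one extra table per time point, with no new data. One caution: SAP 1.6 says all available data are extracted, while Protocol 14.2.1 says some are collected only within windows, so a usable pre-SSI value may be lacking for some early SSIs. The worst-rank and no-change versions do not need one. The supporting figure is likely to be somewhat less favourable, and the assigned values are conventions.

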10.3 Ocular and Glaucoma Medical History

Ocular history of the selected eye will be collected, such as glaucoma diagnosis, previous ocular and glaucoma procedures, previous ocular medications (including whether or not eye is treated with Diamox on the day when decision was taken to implant XEN 45 Gel Stent) and ocular pathologies observed at baseline. Glaucoma stage at baseline will be determined by investigators based on visual field assessment.

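### The baseline exclusion for the IOP-change analyses names only Diamox and so is narrower than the oral drug classes the SAP itself provides for

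*SAP*

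**What the plan says.** Protocol 14.2.4 limits the primary Year 3 analysis to eyes that "were not treated with Diamox on the day when decision was taken to implant XEN 45 Gel Stent". Protocol 14.2.5 applies the same limit to the Year 4 change and to the 20% reduction and IOP-threshold summaries. SAP 4.4 repeats it for Months 12, 24, 36 and 48, keeping "those who were not treated with Diamox on the day when decision was taken to implant XEN 45 Gel Stent", and SAP 4.4.1 carries it into the 20% reduction and IOP-band summaries. No section extends the rule to any other systemic drug.

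SAP 4.3 takes a wider view of oral treatment: "IOP lowering medications (oral) will be described at baseline and post-implantation in the Effectiveness Population by class of medication". The classes given are "carbonic anhydrase inhibitors or alpha-agonist hypotensive agent". These drugs are described only and do not affect who is analysed.

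The information is collected under protocol 10.3, which opens with "Ocular history of the selected eye will be collected" and asks "whether or not eye is treated with Diamox on the day when decision was taken to implant XEN 45 Gel Stent". The medication outcome in both documents (protocol 6.3, SAP 1.5) is the number of topical IOP-lowering drugs.

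**The concern.** Neither document gives a reason for the Diamox exclusion. The evident one is that a systemic drug lowers baseline IOP without appearing in the topical count, so the baseline IOP and the baseline drug count no longer describe the same treatment. That reason applies equally to any other oral IOP-lowering drug.

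As written, two eyes with equally lowered baselines can be treated differently in the primary analysis because of the product recorded. If the drug is stopped after surgery, the retained eye shows too small an IOP fall, the topical count gives no credit for the stop, and the 20% reduction is harder to reach.

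The per-eye wording adds an uncertainty. An oral drug is not specific to one eye, and neither document says how a site should answer when the drug was given because of the other eye.

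**Working it through.** **Scope of the rule against the drugs provided for**

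| Oral drug on the decision day | Provided for in SAP 4.3 | Removed by SAP 4.4 |
|---|---|---|
| Diamox | yes | yes |
| Another oral carbonic anhydrase inhibitor | yes | not as written; yes if Diamox is shorthand for the class |
| Oral alpha-agonist agent | yes | no, on either reading |

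The last row does not depend on how Diamox is read.

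**The plan's own figure.** Protocol 14.1 gives a mean change of -5.6 mmHg, SD 6.32, n = 60. Half-length = 1.96 × 6.32 / √60 = 1.60 mmHg, so the interval is -7.2 to -4.0, as stated. It is not in dispute and serves here as the yardstick.

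**Effect on one retained eye.** Let d be the amount by which the systemic drug lowers IOP.
- Drug at baseline, stopped by follow-up: observed change = true change + d, so the reduction looks smaller by d.
- Drug at both visits, unchanged: the two effects cancel and the error is zero.
- Drug at follow-up only: observed change = true change − d, so the reduction looks larger by d. The rule looks only at the decision day and keeps these eyes too.

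In the first case the IOP needed to meet the 20% criterion falls from 0.8 × B to 0.8 × (B − d), where B is the baseline without the systemic drug. For d = 3–6 mmHg the target is 2.4–4.8 mmHg stricter. The fixed IOP bands do not use baseline IOP, so for them the rule only affects which eyes are counted.

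**Effect on the mean.** With a share f of analysed eyes in the first case, shift = f × d. The documents give neither f nor d, so both are assumed:

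| f | d = 3 mmHg | d = 6 mmHg |
|---|---|---|
| 2% | 0.06 | 0.12 |
| 5% | 0.15 | 0.30 |

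Against the half-length: 0.06 / 1.6 = 4% and 0.30 / 1.6 = 19%. The shift is proportional to f, so 10% of eyes would give 0.30–0.60 mmHg (19–38%).

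**Cost in eyes.** Removing 2–5% of 60 is 60 × 0.02 = 1.2 to 60 × 0.05 = 3 eyes. With 57 eyes the half-length is 1.96 × 6.32 / √57 = 1.64 mmHg. Keeping 60 after the exclusion needs 60 / 0.98 to 60 / 0.95, that is 62 to 64 eyes with three years of follow-up.

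**The case against.** The case for leaving the rule alone has several parts.

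- SAP 4.3 is a table layout covering baseline and post-implantation together. It does not show that any eye was on an oral alpha-agonist, or on a carbonic anhydrase inhibitor other than Diamox, at baseline. This is right as to frequency, which may be zero. It does not alter the rule: any such eye would pass.
- The SAP 4.4 sentence on counting by class leaves out the word topical and lists carbonic anhydrase inhibitors, so an oral drug of that class might be counted. That is a fair point about loose wording. The outcome definitions still say topical, and oral alpha-agonists gain nothing from it unless the sympathomimetic class is also read to include oral drugs.
- The bias is small, runs against the device, and sits in a single-arm, mainly descriptive study. This stands, and it limits the weight of the point.

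Three stronger readings are tempting, and the documents do not support them. A reader might infer that eyes of patients given Diamox for the fellow eye do stay in. The eCRF question and its instructions are not in the documents, and a site could equally answer yes because the drug is systemic; such eyes may stay in, no more. A reader might infer that the plan's stated aim is change from a topically medicated baseline. Both documents say only that the baseline is medicated; topical qualifies the drug count. A reader might also infer that each affected eye loses the whole drug effect. That holds only if the drug was stopped before the follow-up visit.

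**Conclusion.** The point holds in a limited form. The filter for the primary and related analyses names one product, while the SAP makes room for oral drugs in two classes. Even on the generous reading of Diamox as a class label, eyes on an oral alpha-agonist are kept with a baseline lowered by a drug outside the topical count.

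The size is unknown. On the assumed 2–5% of eyes and 3–6 mmHg effect, and with the drug stopped by Month 36, the mean reduction is understated by 0.06–0.30 mmHg. That would not overturn a projected reduction of 5.6 mmHg. Fellow-eye use is an ambiguity in the protocol wording, not a shown error. Systemic use at follow-up is a separate gap that works the other way, towards overstating the reduction. The change is worth making because it corrects a stated rule at little cost, not because the expected bias is large.

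**What to change.** In SAP 4.4 and 4.4.1, and in protocol 14.2.4 and 14.2.5, replace the Diamox condition with: *patient not taking any oral or other systemic IOP-lowering drug on the baseline day*. Derive it from the oral-medication records that SAP 4.3 already tabulates at baseline in the same Effectiveness Population. For paired eyes with the same decision date, apply a yes for either eye to both.

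Add a sensitivity analysis that leaves out eyes on a systemic IOP-lowering drug at the analysed follow-up visit. State in SAP 4.4 whether the class-based count is topical only. The qualified and complete success paragraph in SAP 4.4.1 does not repeat the Diamox condition, so the new wording will not reach it unless the SAP says that it applies there.

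The cost is one changed filter, one extra table and possibly a few eyes fewer in the primary analysis. One gap may remain: where the fellow eye is not enrolled, a drug prescribed for it may not have been recorded. It could not be recovered, because protocol 12 and 14.3.3 rule out queries on the anonymised data. The report should say so.
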